## **7. PLANNED ANALYSIS**

For End-Of-Text (EoT) tables of parameters [REDACTED], the set of summary statistics is: N / Mean / Standard Deviation SD / Min / Median / Max.

For tables that are provided for endpoints with some extreme data, median, quartiles and percentiles should be preferred to mean, standard deviation, minimum and maximum.

In general, means, medians, and quantiles are presented to one more decimal place than the raw data, whereas SDs are presented to two more decimal places than the raw data. Minima and maxima are presented to the same number of decimal places as the raw data.

Tabulations of frequencies for categorical data will include all possible categories (including categories with zero count) and will display the number of observations in a category as well as the percentage (%) relative to the respective treatment group (unless otherwise specified, all subjects in the respective subject set whether they have non-missing values or not).

The precision for percentages should be one decimal point. The category missing will be displayed only if there are actual missing values.

If applicable, conversion from days to weeks, months and years follows the rules below:

- $\text{weeks} = \text{days} \div 7$
- $\text{months} = 12 \times \text{days} \div 365.25$
- $\text{years} = \text{days} \div 365.25$

### **7.1 DEMOGRAPHIC AND OTHER BASELINE CHARACTERISTICS**

Only descriptive statistics are planned for this section of the report.

### **7.2 CONCOMITANT DISEASES AND MEDICATION**

Only descriptive statistics are planned for this section of the report.

Concomitant diseases will be coded based on the most current version of MedDRA. A summary of concomitant diseases will be provided by treatment group, system organ class (SOC), and preferred term (PT).

Concomitant medication will be coded according to WHO DD and classified by the Anatomical, Therapeutic, Chemical (ATC) classification system. Concomitant medication will be summarized separately for psychoactive medications.

### **7.3 TREATMENT COMPLIANCE**

Only descriptive statistics are planned for this section of the report. See [Section 5.4](#) for definitions of treatment compliance and CCT compliance/exposure.

## 7.4 PRIMARY ENDPOINT(S)

### 7.4.1 Primary analysis of the primary endpoint(s)

The primary analysis is a restricted maximum likelihood (REML) based approach using the following mixed model with repeated measurements (MMRM) comparing the change from baseline in MCCB neurocognitive composite T-score after 12 weeks of treatment:

$$y_{ijkm} = \tau_{jk} + \beta_j X_i + \phi_m + \gamma Z_i + e_{ij}$$

$$e_{ij} \sim N(\mathbf{0}, \Sigma)$$

where

- $y_{ijkm}$  = response variable for subject  $i$  in age stratum  $m$  at visit  $j$  receiving treatment  $k$ ,
- $\beta_j$  = coefficient of baseline effect at visit  $j$ ,
- $X_i$  = baseline MCCB neurocognitive composite T-score of subject  $i$ ,
- $\tau_{jk}$  = effect of treatment  $k$  at visit  $j$ ,
- $\phi_m$  = effect of age stratum  $m$
- $\gamma$  = coefficient of change from screening to baseline effect,
- $Z_i$  = change from screening to baseline in MCCB neurocognitive composite T-score
- $e_{ij}$  = random error associated with visit  $j$  of subject  $i$ , independently distributed across subjects,
- $\Sigma$  = unstructured variance-covariance matrix.

The model will include fixed, categorical effects of treatment at each visit, fixed continuous effect of baseline at each visit, fixed effects of age strata ( $\leq 40$  vs.  $> 40$ ), and fixed continuous effect of change in MCCB neurocognitive composite score from screening to baseline. Visit will be treated as the repeated measure with an unstructured variance-covariance matrix used to model the within-patient measurements.

Denominator degrees of freedom will be calculated using Kenward-Roger approximation. The primary treatment comparison will be the contrast between the two treatments at the endpoint visit, i.e. Week 12.

The primary analysis will be performed on FAS. Patients will be analysed according to the actual age stratum they belong to, regardless of any treatment mis-assignment due to wrong stratum identification because such an error would have occurred before randomization and is therefore consistent with regulatory guidance.

In the event of non-convergence, the following methods will be attempted in order:

1. Add the 'singular=1e-10' option in the model statement, to raise the threshold at which columns are declared linearly dependent from the default value of 1e-12.
2. Set 'maxiter=100' in PROC MIXED statement, to increase the number of convergence iterations from a default of 50.
3. Set 'scoring=4' to specify the use of Fisher scoring algorithm in the first 4 iterations.

4. Include the statement 'performance nothread' to remove multi-threading from calculations.

## 7.5 SECONDARY ENDPOINT(S)

### 7.5.1 Key secondary endpoint(s)

This section is not applicable as no key secondary endpoint has been specified in the protocol.

### 7.5.2 (Other) Secondary endpoint(s)

#### 7.5.2.1 Primary analysis of the secondary endpoints

Primary analysis of the secondary endpoints will be conducted on FAS. Estimated least squares mean difference between the two treatment arms will be provided together with 95% confidence intervals. Statistical model and estimation method for each secondary endpoint are described below.

#### MCCB overall composite T-score

The primary analysis of change from baseline in MCCB overall composite T-score after 12 weeks of treatment will be a REML based approach using the same MMRM as in [Section 7.4.1](#). The baseline and change-from-screening-to-baseline covariates,  $X_i$  and  $Z_i$ , will be replaced by their overall composite T-score version.

#### SCoRS interviewer total score

The primary analysis of change from baseline in SCoRS interviewer total score after 12 weeks of treatment will be an ANCOVA based approach using the following model:

$$y_{ikm} = \tau_k + \beta X_i + \phi_m + e_i$$

$$e_i \sim N(0, \sigma^2)$$

where

- $y_{ikm}$  = response variable for subject  $i$  in age stratum  $m$  receiving treatment  $k$ ,  
 $\beta$  = coefficient of baseline effect,  
 $X_i$  = baseline value of subject  $i$ ,  
 $\tau_k$  = effect of treatment  $k$ ,  
 $\phi_m$  = effect of age stratum  $m$   
 $e_i$  = random error associated with subject  $i$ , independently distributed ,  
across subjects

#### PANSS total score

The primary analysis of change from baseline in PANSS total score after 12 weeks of treatment will be a REML based approach using the following simplified MMRM from that in [Section 7.4.1](#):

$$y_{ijkm} = \tau_{jk} + \beta_j X_i + \phi_m + e_{ij}$$

where  $X_i$  = baseline score of subject  $i$ , while the other covariates and parameters are same as defined in Section 7.4.1.

## **7.7 EXTENT OF EXPOSURE**

Extent of exposure will be summarized for the treated set using descriptive statistics for days on treatment as well as frequency and percentage of subjects in the following categories: <30 days, 30 – 41 days, 42 – 59 days, 60 – 89 days,  $\geq$  90 days.

Exposure to CCT will be summarized using descriptive statistics as described in [Section 5.4](#).

## **7.8 SAFETY ANALYSIS**

All safety analyses will be performed on the treated set.

### 7.8.1 Adverse Events

Unless otherwise specified, the analyses of AEs will be descriptive in nature. All analyses of AEs will be based on the number of subjects with AEs and not on the number of AEs. The reporting and analysis of AEs will follow the BI guideline (2). AEs will be coded with the latest version of MedDRA.

The analysis of AEs will be based on the concept of treatment emergent AEs. For this study, the residual effect period (REP) is defined as 11 days after the last dose of trial medication. That means that all AEs occurring between first drug intake till 11 days after last drug intake will be assigned to the “on-treatment” period. All AEs occurring before first drug intake will be assigned to ‘screening’ and all AEs occurring after last drug intake + 11 days will be assigned to ‘follow-up’ (for listings only). For details on the treatment definition, see [Section 6.1](#).

#### Adverse events of special interest (AESIs)

[figure not shown]
As defined in CTP Section 5.2.6.1, AESI includes hepatic injury defined by the following alterations of hepatic laboratory parameters:

- an elevation of AST (aspartate transaminase) and/or ALT (alanine aminotransferase) >3-fold ULN combined with an elevation of total bilirubin >2-fold ULN measured in the same blood draw sample, or
- aminotransferase (ALT, and/or AST) elevations  $\geq 10$ -fold ULN.

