Cancers of new histology and exacerbations of existing cancer must be classified as a serious event regardless of the time since discontinuation of the drug and must be reported as described in [Section 5.2.6.2](#), sub-sections “AE Collection” and “AE reporting to sponsor and timelines”.

In accordance with the European Medicines Agency initiative on Important Medical Events, Boehringer Ingelheim has set up a list of further AEs, which by their nature, can always be considered to be “serious” even though they may not have met the criteria of an SAE as defined above.

The latest list of “Always Serious AEs” can be found in the eDC system. These events should always be reported as SAEs as described above.

Adverse events of special interest (AESIs)

The term AESI relates to any specific AE that has been identified at the project level as being of particular concern for prospective safety monitoring and safety assessment within this trial, e.g. the potential for AEs based on knowledge from other compounds in the same class. AESIs need to be reported to the sponsor’s Pharmacovigilance Department within the same timeframe that applies to SAEs, please see above.

The following are considered as AESIs:

Hepatic injury

A hepatic injury is defined by the following alterations of hepatic laboratory parameters:

- an elevation of AST (aspartate transaminase) and/or ALT (alanine aminotransferase) ≥ 3 fold ULN combined with an elevation of total bilirubin ≥ 2 fold ULN measured in the same blood draw sample, or
- aminotransferase (ALT, and/or AST) elevations ≥ 10 fold ULN

These lab findings constitute a hepatic injury alert and the patients showing these lab abnormalities need to be followed up according to the “DILI checklist” provided in the eDC system.

In case of clinical symptoms of hepatic injury (icterus, unexplained encephalopathy, unexplained coagulopathy, right upper quadrant abdominal pain, etc.) without lab results (ALT, AST, total bilirubin) available, the investigator should make sure these parameters are analysed, if necessary in an unscheduled blood test. Should the results meet the criteria of hepatic injury alert, the procedures described in the DILI checklist should be followed.

Intensity (severity) of AEs

The intensity (severity) of the AE should be judged based on the following:

Mild:	Awareness of sign(s) or symptom(s) that is/are easily tolerated
Moderate:	Sufficient discomfort to cause interference with usual activity

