#### Other significant AE (according to ICH E3)

According to ICH E3 (6), AEs classified as "other significant" needs to be reported and will include those non-serious and non-significant AEs with

1. ‘action taken = discontinuation’ or ‘action taken = reduced’; or
2. marked haematological and other lab abnormalities or lead to significant concomitant therapy as identified by the Clinical Monitor / Investigator during medical quality review at a trial oversight meeting (TOM).

An overall summary of AEs will be presented.

The frequency of subjects with AEs will be summarised by treatment, primary system organ class and PT. Separate tables will be provided for subjects with SAEs, AEs leading to treatment discontinuation, AEs of at least moderate severity and related AEs.

The system organ classes will be sorted by default alphabetically, PTs will be sorted by frequency (within SOC). Customized sorting orders may also be used based on trial needs, e.g. SOC sorted by frequency.

Separate tables will be provided for the following AEs:

- drug-related AEs
- serious AEs (SAEs)
- drug-related SAEs
- AESIs
- Other significant AE (according to ICH E3)
- AEs leading to death
- AEs leading to discontinuation of trial medication
- AEs occurred with >2% incidence in the preferred term
- AEs by intensity
- AEs occurred during the follow-up period.
- AEs related to COVID-19

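### SAP 7.8.1 cites the protocol's hepatic-injury definition but, as printed, makes the 3-fold and 2-fold cut-offs of the combined criterion strict instead of inclusive

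*SAP*

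**What the plan says.** Protocol 5.2.6.1 lists one AESI, hepatic injury, with two alternative criteria. The combined criterion is AST and/or ALT "≥ 3 fold ULN combined with an elevation of total bilirubin ≥ 2 fold ULN measured in the same blood draw sample". The stand-alone criterion is "aminotransferase (ALT, and/or AST) elevations ≥ 10 fold ULN". All three limits are inclusive. Meeting either criterion starts the DILI checklist, and "AESIs need to be reported to the sponsor’s Pharmacovigilance Department within the same timeframe that applies to SAEs".

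SAP 7.8.1 introduces its own list with "As defined in CTP Section 5.2.6.1, AESI includes hepatic injury defined by the following alterations of hepatic laboratory parameters". Its combined criterion then reads AST and/or ALT ">3-fold ULN combined with an elevation of total bilirubin >2-fold ULN measured in the same blood draw sample". For the stand-alone criterion, "aminotransferase (ALT, and/or AST) elevations", it keeps the inclusive sign at 10-fold.

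Later in 7.8.1 the SAP says "Separate tables will be provided for the following AEs", and AESIs are on that list. The visible text neither gives a reason for the strict signs nor describes them as a departure from the protocol.

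**The concern.** A SAP that names the protocol section as the source of a case definition should reproduce that definition. Here two of the three limits change from inclusive to strict. The third does not, so this is not a general change of convention in the SAP.

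What is at stake is agreement between two counts. Sites identify and report hepatic-injury AESIs under the protocol rule. If the AESI table were programmed from laboratory data under the SAP rule, a patient on a boundary could be in the pharmacovigilance record and not in the report's AESI table. Hepatic injury is the only AESI listed, so that table depends on this definition.

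**Working it through.** The plan gives no figure to reproduce. The check compares the two definitions as logical rules.

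**Notation.** Let *a* be the larger of AST and ALT as a multiple of its ULN, and *b* total bilirubin as a multiple of ULN in the same sample.

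- Protocol 5.2.6.1: (*a* ≥ 3 and *b* ≥ 2) or *a* ≥ 10
- SAP 7.8.1 as printed: (*a* > 3 and *b* > 2) or *a* ≥ 10

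**Where they differ.** Every case that meets the SAP rule also meets the protocol rule, so the SAP rule is never wider. The cases that meet only the protocol rule are:

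- (a) *a* = 3 with *b* ≥ 2
- (b) *b* = 2 with 3 ≤ *a* < 10

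**Check on a grid around the limits** (6 values of *a* by 3 values of *b*, 18 points):

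| *a* | *b* = 1.9 | *b* = 2 | *b* = 2.1 |
|---|---|---|---|
| 2.9 | neither | neither | neither |
| 3 | neither | **protocol only** | **protocol only** |
| 3.1 | neither | **protocol only** | both |
| 9.9 | neither | **protocol only** | both |
| 10 | both | both | both |
| 10.1 | both | both | both |

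Four of the 18 points are classified differently: (3, 2), (3, 2.1), (3.1, 2) and (9.9, 2). All four are AESIs under the protocol and not under the SAP text. The grid was chosen to sit on the limits, so 4 of 18 is not a frequency. With ≥ at both SAP cut-offs the two rules are identical and no point differs.

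**Can an exact multiple occur?** The documents give no reference limits, so this is an illustration under assumptions. With an ALT ULN of 40 U/L reported in whole units, 3 × 40 = 120 U/L is exactly 3-fold. With a bilirubin ULN of 1.2 mg/dL reported to 0.1, 2 × 1.2 = 2.4 mg/dL is exactly 2-fold. More generally, if the ULN is itself a value on the laboratory's reporting scale, its 2-fold and 3-fold multiples are too. This shows that a boundary value is possible. It says nothing about how likely one is, and the documents give no rate of combined elevations from which to estimate it.

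**The case against.** Five arguments stand against giving this much weight.

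- **The table may not use this rule.** No visible text says that the AESI table is derived from laboratory values. SAP 7.8.1 lists AESIs among the adverse-event tables, and protocol 5.2.6.1 treats them as events that sites report. If the table uses site-reported AESIs, a boundary case is counted whatever sign the SAP prints. This stands, and it makes any effect on the count conditional.
- **The SAP defers to the protocol.** It cites the section and states no wish to redefine the event, so the likeliest explanation is a slip in transcription. This also stands, and it is why the correction should follow the cited source. It does not make the printed definition right.
- **The sign may have been lost when the PDF was read.** This cannot be fully excluded. It is unlikely, because ≥ is intact in the next item of the same list, and ≥ or ≤ is intact in SAP 5.2.2, 6.6, Table 6.7: 1 and 7.7.
- **The patient would not disappear from the report.** SAP 7.8.2 gives laboratory values by visit and shift tables from baseline to worst value. Protocol 7.3.4 summarises out-of-range and clinically relevant values. Any reported event enters the general adverse-event tables. The DILI checklist and expedited reporting follow the protocol and are unaffected. All of this stands.
- **Some stronger readings fail.** A reader might infer that any value at exactly 3-fold or 2-fold is classified differently. That is not so. ALT at exactly 3-fold with normal bilirubin is an AESI under neither document, and bilirubin at exactly 2-fold with ALT at 10-fold or more is one under both. A reader might also infer that the AESI table will undercount, or that a single boundary case would be the whole hepatic signal. The documents support neither: the table's source is not stated, and no base rate is given.

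**Conclusion.** The inconsistency is real as printed. SAP 7.8.1 attributes to protocol 5.2.6.1 a combined criterion that is narrower than the one written there. The difference runs in one direction and is confined to situations (a) and (b) above.

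The consequence depends on something the visible text does not settle. If the AESI table is derived from laboratory values with the SAP wording, it could omit a case that sites must report. If it is built from site-reported AESIs, the count does not change, but the SAP then describes its own table wrongly. Either way the text needs correcting.

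The point is minor. It concerns exact boundary values only, the safety analyses are descriptive, and no efficacy result is touched. No expected number of affected patients can be given from the documents. The conclusion assumes that the strict signs are in the SAP itself and were not introduced when its text was extracted.

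**What to change.** First confirm the two signs in the source SAP. Then reconcile SAP 7.8.1 with protocol 5.2.6.1, the definition it says it uses, by printing ≥ at the 3-fold and 2-fold cut-offs. The 10-fold item stays as it is. Align any programmed AESI flag with the corrected text and, if this is not already stated elsewhere, add a sentence saying whether the AESI table comes from laboratory values or from site-reported events.

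The cost is two symbols in the SAP and, if a flag is programmed, one line of code. The protocol, site procedures and data collection do not change. Compared with the strict rule, the AESI count can only stay the same or rise.

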#### Other significant AE (according to ICH E3)

According to ICH E3 (6), AEs classified as "other significant" needs to be reported and will include those non-serious and non-significant AEs with

1. ‘action taken = discontinuation’ or ‘action taken = reduced’; or
2. marked haematological and other lab abnormalities or lead to significant concomitant therapy as identified by the Clinical Monitor / Investigator during medical quality review at a trial oversight meeting (TOM).

An overall summary of AEs will be presented.

The frequency of subjects with AEs will be summarised by treatment, primary system organ class and PT. Separate tables will be provided for subjects with SAEs, AEs leading to treatment discontinuation, AEs of at least moderate severity and related AEs.

The system organ classes will be sorted by default alphabetically, PTs will be sorted by frequency (within SOC). Customized sorting orders may also be used based on trial needs, e.g. SOC sorted by frequency.

Separate tables will be provided for the following AEs:

- drug-related AEs
- serious AEs (SAEs)
- drug-related SAEs
- AESIs
- Other significant AE (according to ICH E3)
- AEs leading to death
- AEs leading to discontinuation of trial medication
- AEs occurred with >2% incidence in the preferred term
- AEs by intensity
- AEs occurred during the follow-up period.
- AEs related to COVID-19

## **7.8.2 Laboratory data**

The analyses of laboratory data will be descriptive in nature and will be based on BI standards [\(5\)](#).

Descriptive statistics for laboratory values will be derived and displayed visit-by-visit using converted values. Shift tables of change in laboratory parameters between baseline and worst value on treatment, between baseline and last value on treatment, and between worst and last value on treatment will also be presented.

In addition, the following will be presented for haemoglobin (Hb):

- shift tables of change in Hb between last value on treatment and last value post-treatment,
- spaghetti plots of change in Hb from baseline across time with time trend of mean and standard error,

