Statistical methods	
Restricted Maximum Likelihood (REML)-based Mixed-effect Model Repeated Measures (MMRM) analysis will be used as the primary analysis for the primary efficacy endpoint of change from baseline in the MCCB neurocognitive composite score after 12 weeks of treatment. This model will include fixed effects of treatment, age stratification factor, visit, as well as the continuous fixed covariates of baseline MCCB neurocognitive composite score, change from screening to baseline MCCB neurocognitive composite score, baseline-by-visit interaction and treatment-by-visit interaction. Patient will be treated as random effect. The unstructured variance-covariance structure will be used to model the within-patient errors.
 
For the secondary efficacy endpoint of change from baseline in the overall MCCB composite score or PANSS total score after 12 weeks of treatment, an MMRM model same as or similar to that used for the primary endpoint will be fitted. For change from baseline in SCoRS score after 12 weeks of treatment, an ANCOVA model will be fitted.
 
Descriptive statistics and exploratory analyses will be provided for safety data and other efficacy endpoints.

FLOW CHART

Trial Periods and Procedures	Screening Period (*)	Randomized Treatment Period					End of Study
		2 ¹	3	4	5	6 (e)EoT ^{1,2}	
Visit	1 Screening						Follow-up ²
Weeks			3	6	9	12	16
“Days” from first randomized treatment	-28 to -1	0 (***)	21	42	63	84	EoT +28
Time window for visits	28 days	N/A	±3 days	±3 days	±3 days	+3 days	+7 days
Informed consent(**)	X						
Demographics	X						
Medical history	X						
Physical examination	X	X		X		X	X
Vital signs	X	X		X		X	X
Height	X						
Weight	X	X		X		X	X
Safety Laboratory tests (urine/blood)	X	X		X ¹³		X ¹³	X ¹⁴
Pregnancy test ³	X	X	X	X	X	X	
Drug screen test (urine)	X	X		X		X	
12-lead ECG ⁴	X	X		X		X	X
In-/exclusion criteria	X	X					
Contact IRT	X	X	X	X	X	X	
Randomization		X					
Dispense and administer trial drug		X	X	X	X		
Termination of trial drug ⁵						X	
██████████			█	█	█	█	
MCCB	X ⁷	X		X		X	
C-SSRS ⁸	X	X	X	X	X	X	X
PANSS ⁹	X	X		X		X	
SCoRS ⁹	X	X				X	
██████████		█				█	
M.I.N.I.	X						
██████████		█				█	
Adverse events(*****)	X	X	X	X	X	X	X
Compliance check (study drug)			X	X	X	X	
Concomitant therapy	X	X	X	X	X	X	X
CCT device and related equipment distributed (if needed); patient trained on CCT program	X						

Trial Periods and Procedures	Screening Period (*)	Randomized Treatment Period					End of Study

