¹² Preferably within 7 days after written informed consent signed (enrolment), patients that meet eligibility criteria (according to available information) will begin the CCT run-in; this will be considered day 1 of the CCT run-in. During the screening period, once eligibility based on CCT run-in is established, the patient should not complete any further CCT until they are randomized to the treatment period. Note for re-screened patients: If CCT run-in compliance is confirmed but patient is a screen failure for another reason and is later re-screened, then the CCT run-in should not be repeated during re-screening.

¹³ Any hemoglobin decrease >20 g/L (2 g/dL) since baseline (Visit 2) or leading to symptoms of anemia (e.g. dyspnea, dizziness, etc) will require safety follow-up with safety lab at the next visit(s), or earlier if considered necessary by the investigator.

¹⁴ All patients with hemoglobin drop below 100 g/L (10 g/dL) or absolute decrease >20 g/L (2 g/dL) since baseline (Visit 2) will need to be followed up post-end of study until value returns to baseline/normal value, or resolution (per investigator's judgement).

For potential modifications of trial conduct in case of restrictions due to COVID-19, please refer to [Section 4.1.4](#), [Section 6.2](#), [Section 8.2](#) and [Section 10.5](#).

TABLE OF CONTENTS

TITLE PAGE	1
CLINICAL TRIAL PROTOCOL SYNOPSIS	2
FLOW CHART	6
TABLE OF CONTENTS	9
ABBREVIATIONS	12
1. INTRODUCTION.....	14
1.1 MEDICAL BACKGROUND.....	14
1.2 DRUG PROFILE	15
1.3 RATIONALE FOR PERFORMING THE TRIAL	17
1.4 BENEFIT - RISK ASSESSMENT.....	18
2. TRIAL OBJECTIVES AND ENDPOINTS.....	22
2.1 MAIN OBJECTIVES, PRIMARY AND SECONDARY ENDPOINTS.....	22
2.1.1 Main objectives.....	22
2.1.2 Primary endpoint(s).....	22
2.1.3 Secondary endpoint(s)	22
	
3. DESCRIPTION OF DESIGN AND TRIAL POPULATION	24
3.1 OVERALL TRIAL DESIGN AND PLAN	24
3.2 DISCUSSION OF TRIAL DESIGN, INCLUDING THE CHOICE OF CONTROL GROUP(S)	25
3.3 SELECTION OF TRIAL POPULATION	25
3.3.1 Main diagnosis for trial entry	26
3.3.2 Inclusion criteria	26
3.3.3 Exclusion criteria	27
3.3.4 Withdrawal of patients from therapy or assessments	30
3.3.4.1 Withdrawal from trial treatment	30
3.3.4.2 Withdrawal of consent for trial participation.....	31
3.3.4.3 Discontinuation of the trial by the sponsor	31
4. TREATMENTS.....	33
4.1 INVESTIGATIONAL TREATMENTS	33
4.1.1 Identity of BI investigational product(s) and comparator product(s)	33

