Section to be changed		FLOW CHART footnote (*****)
Description of change		Instruction that, following patient's trial participation, only any cancers of new histology and exacerbations of existing cancer, trial treatment related SAEs and trial treatment related AESIs of which the investigator may become aware of should be reported and only via the BI SAE form, in alignment with wording in Section.5.2.6.2
Rationale for change		Additional reminder to investigator
Section to be changed		FLOW CHART footnotes 1, 5 and 6
Description of change		Added clarification that split visits are to be done on 2 consecutive calendar days
Rationale for change		Avoid the possible misinterpretation of the word "sequential" that could lead to a split visit being done a Friday and the following Monday
Section to be changed		FLOW CHART footnote 13
Description of change		Additional note that any hemoglobin decrease >20 g/L (2 g/dL) since baseline (Visit 2) or leading to symptoms of anemia (e.g. dyspnea, dizziness, etc) will require safety follow-up with safety lab at the next visit(s), or earlier if considered necessary by the investigator
Rationale for change		Reminder for investigators, in alignment with new text in Section 5.2.6.2
Section to be changed		FLOW CHART footnote 14
Description of change		Additional note that all patients with hemoglobin drop below 100 g/L (10 g/dL) or absolute decrease >20 g/L (2 g/dL) since baseline (Visit 2) will need to be followed up post-end of study until value returns to baseline/normal value, or resolution (per investigator's judgment)
Rationale for change		Reminder for investigators, in alignment with new text in Section 6.2.3
Section to be changed		1.2
Description of change		Various changes to Drug Profile wording based on updated IB

Rationale for change		Alignment with updated Investigator's Brochure
Section to be changed		1.4
Description of change		Various changes to Benefit-Risk Assessment wording based on updated IB
Rationale for change		Alignment with updated Investigator's Brochure
Section to be changed		3.3
Description of change		Updated planned number of trial centres and countries participating in the trial, indicated as range
Rationale for change		To reflect current planned number of trial centres and countries participating in the trial
Section to be changed		3.3.2 inclusion criterion 4
Description of change		Remove reference to psychotropic medications in general with examples

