## 6.7 BASELINE, TIME WINDOWS AND CALCULATED VISITS

In general, baseline value will be the measurement taken on the day of randomization (Visit 2), and prior to the first study medication administration. If this value is not available, the measurement at the screening visit (Visit 1) will be used, except for MCCB assessments.

Baseline for MCCB neurocognitive composite score and related endpoints is defined as the measurements taken at randomization (Visit 2), and prior to the first administration of the study medication.

Analysis visit will be used for by-visit summaries and analysis of efficacy endpoints. Study day windows for mapping to analysis visits are presented in Table 6.7: 1. Actual study day will be calculated starting with day of randomization as Day 1. If more than one assessment is mapped to the same post-baseline analysis visit, the closest assessment to the planned study day will be used. In case of a tie, the earlier assessment will be used.

Table 6.7: 1 Analysis visit windows

Analysis visit	Nominal Timepoint	Planned study day	Actual study day window	
			MCCB*, PANSS	Other efficacy assessments
2	Baseline	1	≤1	≤1
4	Week 6	43	2 – 60	
6/EoT	Week 12	85	≥61	≥2

\*MCCB assessments taken >12 days after the last study medication intake will not be included in the analysis.

Safety endpoints will be summarized based on nominal visits as reported in the CRFs. No re-labelling to analysis visits will be performed.

In subject data listings, all data at scheduled or unscheduled timepoints will be presented.

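### The SAP's haemoglobin mean trend is not limited to labs scheduled for everyone, so if triggered samples are recorded under Visit 5 it can show an artificial Week 9 dip and rebound

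*SAP*

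**What the plan says.** **Sampling.** In the protocol Flow Chart, the safety laboratory row is marked at Visit 1, Visit 2 (baseline), Visit 4 (Week 6), Visit 6/(e)EoT (Week 12) and Follow-up. The cells for Visit 3 (Week 3) and Visit 5 (Week 9) are empty. Footnote 13 is attached to the Visit 4 and (e)EoT cells. Its trigger is "Any hemoglobin decrease >20 g/L (2 g/dL) since baseline (Visit 2) or leading to symptoms of anemia", and a triggered patient "will require safety follow-up with safety lab at the next visit(s), or earlier if considered necessary by the investigator". Footnote 14, attached to the Follow-up cell, and protocol 6.2.3 say that patients with a low or markedly reduced Hb "will need to be followed up post-end of study until value returns to baseline/normal value, or resolution", the last in the investigator's judgement.

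**Analysis.** SAP 6.7: "Safety endpoints will be summarized based on nominal visits as reported in the CRFs", with no re-labelling to analysis visits. SAP 7.8.2 plans visit-by-visit descriptive statistics for laboratory values and, for Hb in particular, "spaghetti plots of change in Hb from baseline across time with time trend of mean and standard error" and "shift tables of change in Hb between last value on treatment and last value post-treatment". It states no restriction to labs scheduled for everyone and no minimum number of patients per time point.

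**The concern.** A fall found at Visit 4 sends the patient to a lab at the next visit, which is Visit 5. Patients without such a fall have no required Hb there. A Week 9 value is thus observed because the Week 6 value was low, and successive Hb values in one patient are correlated. A mean over those patients estimates the mean of the worst fallers, not of the arm. On a line through Weeks 6, 9, 12 and 16 it would look like a trough at Week 9 followed by recovery at Week 12, when everyone is sampled again.

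Hb decrease is a named, dose-dependent risk in protocol 1.4, and this plot is a dedicated output on its time course. The artefact would also affect placebo, where the few patients sampled are equally selected. The plot could therefore suggest a dip in both arms and blur the difference between them.

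**Working it through.** The plan gives no figure to reproduce here: protocol Table 7.7: 1 concerns the cognitive endpoint.

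**Input from the documents.** Mean Hb change at 10 mg in the earlier 12-week schizophrenia study: -3.3 g/L (protocol 1.4). Trigger: change below -20 g/L. Planned arm size: 100.

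**Assumptions, because the documents give no values.** The true mean is constant over time, at -3.3 g/L on drug and 0 on placebo. SD of change is 8 or 10 g/L, and correlation ρ between Week 6 and Week 9 changes is 0.5 or 0.7, jointly normal. Every trigger gives a value recorded at Visit 5, all patients are under Amendment 3, and nobody leaves treatment for low Hb. Symptom-only triggers are ignored.

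**Step 1, share sampled.** z = (-20 - μ)/SD and p = Φ(z).
- Drug, SD 8: z = (-20 + 3.3)/8 = -2.09, p = 0.018, or 1.8 per 100.
- Drug, SD 10: z = -16.7/10 = -1.67, p = 0.048, or 4.8 per 100.
- Placebo: z = -2.5 and -2.0, p = 0.006 and 0.023.

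**Step 2, chance of at least one value among 100.** 1 - (1 - p)^100 is 84% (SD 8) and 99% (SD 10) on drug. On placebo it is about 46% and 90%.

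**Step 3, expected Week 9 mean of those sampled.** E = μ - ρ × SD × φ(z)/Φ(z). On drug, φ(z)/Φ(z) is 2.451 (SD 8) and 2.084 (SD 10). On placebo it is 2.823 and 2.373.

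| SD | ρ | Drug, Week 9 mean sampled | Placebo, Week 9 mean sampled |
|---|---|---|---|
| 8 | 0.5 | -3.3 - 0.5 × 8 × 2.451 = -13.1 | -11.3 |
| 8 | 0.7 | -3.3 - 0.7 × 8 × 2.451 = -17.0 | -15.8 |
| 10 | 0.5 | -3.3 - 0.5 × 10 × 2.084 = -13.7 | -11.9 |
| 10 | 0.7 | -3.3 - 0.7 × 10 × 2.084 = -17.9 | -16.6 |

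Simulation of the same model agrees to within 0.1 g/L.

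**Step 4, what the plot would show.** The drug line drops by 9.8 g/L (13.1 - 3.3) to 14.6 g/L (17.9 - 3.3) at Week 9 and returns to -3.3 at Week 12, with no true change. The drug-placebo gap at Week 9, when both arms have values, is -1.2 to -1.8 g/L by row of the table, against a true -3.3.

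**Step 5, with scheduled visits only.** There is no Week 9 mean, and the drug line stays at -3.3 g/L at Weeks 6, 12 and 16.

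**Post-treatment shift table.** SAP Table 6.1: 2 ends the Follow-up period for safety analysis at the last per-protocol visit. The protocol treats the Follow-up Visit as the individual patient's end of trial. Footnote 14 sampling comes after that, so on a plain reading it lies outside every analysis period. SAP 7.8.2 does not cross-refer to this cut-off.

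**The case against.** **The samples may never enter the Visit 5 mean.** Protocol 5.2.3 has clinically relevant abnormal results confirmed with an unscheduled-visit kit, and footnote 13 allows sampling before the next visit. Samples coded as unscheduled may stay out of by-visit summaries. This stands, and makes the point conditional. But the SAP speaks of unscheduled data only for listings, and footnote 13 names the next visit.

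**Everyone may be sampled at Visit 5.** Protocol 6.2.2 mentions safety lab samples before dosing when describing Visits 3 to 5 together. Protocol 5.2.3, however, refers to the Flow Chart for sampling times, and its Visit 5 cell is empty.

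**Unseen rules may cover it.** SAP 7.8.2 relies on a sponsor laboratory-data standard that is not available, and its Hb list ends with a comma. This limits confidence; only the absence of a visible restriction can be asserted.

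**The size is uncertain and the effect small.** SD, correlation and placebo mean are assumptions. Withdrawal from treatment for low Hb or symptomatic anaemia (protocol 3.3.4.1) would remove some of the largest falls before Visit 5. The display is descriptive, individual lines are visible, and the SAP's standard summary set includes N. All of this stands; the scheduled visits and the baseline-to-worst and baseline-to-last shift tables still carry the main Hb assessment.

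**Two stronger readings a reader might infer are not supported.**
- That the post-treatment shift table shows recovery by design in nearly all affected patients. Table 6.1: 2 on a plain reading excludes the post-study samples, and follow-up may also end on the investigator's judgement. In a simulation with no true recovery (SD 8-12 g/L, ρ 0.5-0.7, resampling until the change was -5 g/L or better, at most 6 repeats), 14-41% of drug patients more than 20 g/L down at Follow-up were still that far down at their last value. Some apparent recovery is ordinary regression to the mean, present with scheduled samples too.
- That the problem arises solely from Amendment 3. That amendment added footnotes 13 and 14, but the general rule in protocol 5.2.3 to repeat clinically relevant abnormal results until they normalise or stabilise is not among its listed changes.

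**Conclusion.** The point holds in conditional form. Required Hb sampling at Visit 5 depends on the outcome, and the SAP's nominal-visit rule, applied literally, would put a mean of those patients on the Hb trend line. If triggered samples are recorded under Visit 5, the drug arm would show about -13 to -18 g/L from about 2-5 patients per 100, against a true -3.3 g/L. This rests on the assumed SD and correlation, and on no withdrawals for low Hb and all patients being under Amendment 3; relaxing either of the last two would generally lower the number sampled. No efficacy result is affected. The change is still worth making, because it removes a selection artefact from a dedicated display of a named drug risk. For the post-treatment shift table, only a minor clarification of the cut-off is needed.

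**What to change.** In SAP 7.8.2:

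- Restrict by-visit Hb statistics and the mean/SE line to the visits at which the protocol schedules a safety lab for everyone (Visits 2, 4, (e)EoT and Follow-up), and show n at each.
- Show triggered or unscheduled Hb values only as individual points on the plot and in listings.
- Keep all values for the baseline-to-worst shift table.
- As a minor clarification, state that the last post-treatment value is taken within the Follow-up period of Table 6.1: 2, up to the scheduled Follow-up Visit, and list samples taken after end of study separately.

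The cost is a few sentences in the SAP and a visit filter in the Hb programs. No new data are needed and patient care does not change.
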